8 SAFETY MANAGEMENT

8.1 Clinical Adverse Events

Septic shock is a complex and life-threatening condition for which we expect a wide range of potential adverse events, including organ dysfunction, hospital-acquired infections, and death, to occur as part of the routine clinical course. In addition, because all intravenous/intraosseous medications, including crystalloid fluids such as NS and LR, can result in intravenous and/or intraosseous extravasation with soft tissue infiltrates, we expect that intravenous and/or intraosseous extravasation with soft tissue infiltrates will occur as part of the routine clinical care for some subjects enrolled in this study. Since all decisions to administer fluids for a specified indication, timing, and/or volume remain at the discretion of the clinical care team, we do not consider intravenous and/or intraosseous extravasation with soft tissue infiltrates to be an unexpected event. Finally, because of the strong existing safety profile of both NS and LR, common clinical use of both fluids to treat septic shock, pragmatic study design with limited, targeted data collection, and because there is no biologic plausible reason to anticipate that adverse events related to study fluid administration should occur remote from fluid administration itself, we will not plan to continuously monitor for clinical adverse events (AEs). Instead, we will monitor for AEs by a chart review that will occur at two time points—1) after the end of the intervention phase and 2) at 5-7 days after the intervention phase (or at hospital discharge, whichever comes first) as shown in Appendix 3. We will limit the time period for determination of AEs to 5-7 days following the end of the administration of study fluid because there is no biologically plausible reason to anticipate that either LR or NS should lead to adverse events remote from the immediate intervention period. We selected a time period of 5-7 days following the end of the intervention period in order to ensure that no clinically significant AEs are missed in this pilot feasibility study in order to better inform a subsequent large randomized multicenter trial.

If AEs are identified, the AE will be reported as they arise as described in Section 8.5 and then will be followed through to resolution or hospital discharge, whichever comes first. In addition, we will also monitor for the specific safety endpoints noted in Section 5.4 that we have *a priori* identified as potential events that may be differentially impacted by use of NS or LR. These safety endpoints will be ascertained through intermittent data collection throughout the intervention and follow-up phases and at hospital discharge or 90 days following randomization, whichever comes first.

8.2 Adverse Event Reporting

Unanticipated problems related to the research involving risks to subjects or others that occur during the course of this study (including SAEs) will be reported to the IRB in accordance with CHOP IRB SOP 408: Unanticipated Problems Involving Risks to Subjects. AEs that are not serious but that are notable, unanticipated, and could involve risks to subjects will be summarized in narrative or other format and submitted to the IRB at the time of continuing review.

8.3 Definition of an Adverse Event

An adverse event is any untoward medical occurrence in a subject who has received an intervention (drug, biologic, or other intervention) and is not anticipated to occur as a part of the routine clinical course of septic shock. Because septic shock is a complex and life-threatening condition for which we anticipate a wide range of potential medical events, including organ dysfunction, hospital-acquired infections, and death, to occur as part of the routine clinical course, there are few events that will be unanticipated. However, the occurrence of an AE does not necessarily have to have a causal relationship with the treatment. An AE can therefore be any unfavorable or unintended sign (including an abnormal laboratory finding, for example), symptom, or disease temporally associated with the use of a medicinal product, whether or not considered related to the medicinal product, that was not anticipated to occur as part of the routine clinical course of septic shock.

All unanticipated AEs (including serious AEs) will be noted in the study records and on the case report form with a full description including the nature, date and time of onset, determination of non-serious versus serious, intensity (mild, moderate, severe), duration, causality, and outcome of the event. AEs that occur within the timeframe noted in Section 8.1 will be followed until either resolution or hospital discharge, whichever occurs first.

Intensity of AEs will be defined as follows:

- Mild: mild event of its type that does not interfere with routine activities
- Moderate: moderate event of its type that interferes with routine activities
- Severe: severe event of its type that makes it impossible to perform routine activities

8.4 Definition of a Serious Adverse Event (SAE)

As noted above, septic shock is a complex and life-threatening condition that commonly causes organ dysfunction, need for invasive medical and surgical therapies (including, but not limited to, mechanical ventilation, renal replacement therapy, plasma exchange, extracorporeal membrane oxygenation, and cardiopulmonary resuscitation), subsequent hospital-acquired infections, and even death. Consequently, the development of new or progressive organ dysfunction, need for invasive medical and surgical therapies (including, but not limited to, mechanical ventilation, renal replacement therapy, plasma exchange, extracorporeal membrane oxygenation, and cardiopulmonary resuscitation), identification of a hospital-acquired infection, and death are all anticipated to occur as part of routine clinical practice for subjects enrolled in this study (see Table 3 below for list of expected and possible unexpected adverse events).

An SAE will be defined as any unanticipated adverse drug experience that results in any of the following outcomes:

- an unanticipated life-threatening event (at risk of death at the time of the event), or
- requires prolongation of existing hospitalization, or
- a persistent or significant disability/incapacity.

Other important unanticipated medical events that may not be life-threatening or require hospitalization may be considered a serious adverse drug event when, based upon appropriate medical judgment, they may jeopardize the subject and may require medical or surgical intervention to prevent one of the outcomes listed in this definition.

A distinction should be drawn between serious and severe AEs. A severe AE is a major event of its type. A severe AE does not necessarily need to be considered serious. For example, nausea which persists for several hours may be considered severe nausea, but would not be an SAE. On the other hand, a stroke that results in only a limited degree of disability may be considered a mild stroke, but would be an SAE.

8.4.1 Relationship of SAE to study drug or other intervention

The relationship of each SAE to the study intervention will be characterized using one of the following terms in accordance with CHOP IRB Guidelines: definitely, probably, possibly, unlikely or unrelated.

8.5 IRB/IEC Notification of SAEs and Other Unanticipated Problems

The Investigator will promptly notify the IRB of all on-site unanticipated, serious Adverse Events that are related to the research activity. Other unanticipated problems related to the research involving risk to subjects or others will also be reported promptly. Written reports will be filed using the eIRB system and in accordance with the timeline below. External SAEs that are both unexpected and related to the study intervention will be reported promptly after the investigator receives the report.

Type of Unanticipated Problem	Initial Notification (Phone, Email, Fax)	Written Report
Internal (on-site) SAEs that are Life Threatening	24 hours	Within 2 calendar days
Internal (on-site) SAEs All other SAEs	7 days	Within 7 business days
Unanticipated Problems Related to Research	7 days	Within 7 business days
All other AEs	N/A	Brief Summary of important AEs may be reported at time of continuing review

8.5.1 Reporting procedures

AEs will only be reported if judged by the investigators to be related to administration of study fluid. SAEs will be reported regardless of whether these are judged to be related to administration of study fluid. See “Adverse Event Reporting” in Appendix 3 for a flow diagram outlining the need for and timing of reporting of AEs and SAEs.

AEs and SAEs to be collected for subjects enrolled in this study are listed in Table 3, along with classification as either expected within the study population of pediatric patients with septic shock or unexpected. All of the events lists in Table 3 could potentially be related to the study fluid intervention, though this determination will be made on a case-by-case basis. Other unexpected events not listed in Table 3 will not be collected unless the clinical care team and/or the study investigators determine that the event may be related to the study fluid intervention.

Table 3: Adverse Events To Be Collected

Event	AE or SAE	Expected in Pediatric Sepsis
Death ¹	SAE	Expected
Cardiac arrest requiring CPR	SAE	Expected
Arrhythmia requiring intervention	AE	Not Expected
Vasoactive infusion	SAE	Expected
Extracorporeal membrane oxygenation (ECMO)	SAE	Expected
Invasive mechanical ventilation	SAE	Expected
Non-invasive mechanical ventilation	AE	Expected
Dialysis (not pre-existing) ¹	SAE	Expected
Liver dysfunction	SAE	Expected
Limb necrosis	SAE	Expected
Brain herniation ²	SAE	Not Expected
Seizure	AE	Not Expected
Pulmonary embolus	SAE	Not Expected
Deep venous thrombosis	AE	Expected
Central venous line clot requiring pharmacologic therapy ²	AE	Expected
Bleeding (not requiring massive transfusion protocol)	AE	Expected
Bleeding (requiring massive transfusion protocol)	SAE	Not Expected

Hospital-acquired infection ³	AE	Expected
Pressure ulcer	AE	Expected
IV infiltrate (grade 3 or 4)	AE	Expected
Rash	AE	Expected
Hyperlacatatemia > 4 mmol/L ²	AE	Expected
Hyperkalemia >6 mEq/L ²	AE	Not Expected
Hypercalcemia (ionized calcium > 1.35 mEq/L or total calcium > 12 mEq/L) ²	AE	Not Expected
Hypernatremia >155 mEq/L ²	AE	Not Expected
Hyponatremia <128 mEq/L ²	AE	Not Expected
Hyperchloremia >110 mEq/L ²	AE	Expected

¹Event also included as pre-specified efficacy outcome

²Event also included as pre-specified adverse outcome

³Includes central line-associated bloodstream infection, urinary tract infection (both catheter-associated and non-catheter-associated), ventilator-associated pneumonia, ventilator-associated tracheitis, hospital-acquired viral infection, surgical site infection, and *C. difficile* colitis)

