3.2 Allocation to Treatment Groups and Blinding

Randomization will be performed using 1:1 permuted blocks. Randomization sequence will be generated prior to the start of the study and will be filed using a series of numbered, opaque envelopes. Envelopes with study arm assignment will be stored in close proximity to crystalloid fluids in the CHOP ED. Treatment allocation will be revealed to the clinical care team after eligibility for enrollment has been determined to be appropriate by asking a member of the care team to open the next sequentially numbered envelope. The number of the envelope and study arm assignment will be recorded in a log after opening the envelope. The clinical team will then be directed to use the assigned study fluid for all subsequent crystalloid fluid administration within the remainder of the study window. Compliance with study fluid administration will be the primary feasibility assessment in this study (Aim 1).

Fluid administration will be open-label and neither the subject nor the care team will be blinded to the allocated treatment assignment. Blinding study fluid is not pragmatic and unlikely to even be possible. In the SPLIT fluid trial, two-thirds of clinicians correctly identified the randomized crystalloid patients received as electrolyte differences following NS or LR provide clear indication of fluid selection.³⁵ However, randomization following study enrollment will help to minimize selection bias that might occur due to pre-enrollment awareness of study group assignment.

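### Sections 8.3 and 8.5.1 disagree on whether unlisted unexpected events need an unblinded relatedness judgment to be recorded; separately, acid-base disturbance and kidney injury short of dialysis are on no safety list

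*Combined protocol and SAP*

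**What the plan says.** **Recording of events.** Section 8.3 defines an adverse event as one that "is not anticipated to occur as a part of the routine clinical course of septic shock", and says it counts "whether or not considered related to the medicinal product". It then states the recording rule: "All unanticipated AEs (including serious AEs) will be noted in the study records and on the case report form", with causality as one of the items described.

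Section 8.5.1 sets a different rule for anything outside Table 3: "Other unexpected events not listed in Table 3 will not be collected unless the clinical care team and/or the study investigators determine" that there may be a link to the study fluid. The same section limits reporting of non-serious events: "AEs will only be reported if judged by the investigators to be related to administration of study fluid". Serious events are to be reported whatever the relatedness judgment.

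On blinding, section 3.2 says that "neither the subject nor the care team will be blinded to the allocated treatment assignment".

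**Choice of safety endpoints.** Section 8.1 describes the section 5.4 endpoints as those "identified as potential events that may be differentially impacted by use of NS or LR". Section 5.4 has nine endpoints: six laboratory abnormalities (lactate, potassium, calcium, high sodium, low sodium, chloride), line clotting with ceftriaxone and LR, therapy for brain herniation, and therapy for thromboembolism. In Table 4 (section 9.4.3), footnote a marks hyperkalemia, acid-base disturbance, acute kidney injury and infection as possibly more common with NS. Table 3 has no acid-base entry, and its only kidney entry is new dialysis, which is also an efficacy outcome in section 5.3. Section 6.3.4 checks completeness of data for the listed safety endpoints only.

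**The concern.** These are two separate defects.

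First, a site cannot follow both recording rules. Under 8.3, causality is a field completed after an event is recorded. Under 8.5.1, for an unlisted event, it decides whether there is a record at all. The people deciding know the arm. If they are readier to suspect one fluid than the other, identical events will be recorded at different rates, and nobody can check this afterwards because the unrecorded events leave no trace. Section 8.1 chose the adverse-event window so that no clinically important event is missed, and the 8.5.1 condition works against that aim.

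Second, two risks meet the plan's own description of a 5.4 endpoint and are left out. Sections 1.3.1 and 1.5 name kidney injury and acidemia among the concerns about NS, and section 1.3.2 discusses kidney injury as a comparative outcome. The 5.4 outcomes are the ones planned for the later multicenter trial. The pilot is the occasion to learn whether they can be obtained from routine charts, and for these two it would not find out.

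**Working it through.** No sample size, power or error-rate figure bears on this point, so there is no plan figure to reproduce. The check compares the sections and adds one illustration.

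**Step 1. The two recording rules for an unexpected event not in Table 3**

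| | Section 8.3 | Section 8.5.1 |
|---|---|---|
| Judged possibly related | recorded | collected |
| Judged unrelated | recorded | not collected |

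The second row is the contradiction. Anaphylaxis, bronchospasm and pulmonary edema are examples of Table 4 risks that Table 3 does not list by name.

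**Step 2. What the 8.5.1 rule could do to counts.** Expected recorded events per arm = 35 × true rate × probability of being recorded. The 35 per arm is from section 6.4. The true rate (the same in both arms) and the recording probabilities are assumptions, because the documents give neither.

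| Recorded, NS / LR | True rate 10% | 20% | 30% |
|---|---|---|---|
| 50% / 50% | 1.75 / 1.75 | 3.5 / 3.5 | 5.25 / 5.25 |
| 40% / 60% | 1.4 / 2.1 | 2.8 / 4.2 | 4.2 / 6.3 |
| 30% / 80% | 1.05 / 2.8 | 2.1 / 5.6 | 3.15 / 8.4 |
| 80% / 30% | 2.8 / 1.05 | 5.6 / 2.1 | 8.4 / 3.15 |

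For example, 35 × 0.20 × 0.30 = 2.1 and 35 × 0.20 × 0.80 = 5.6. A spurious difference appears only if recording differs by arm, and it can go either way.

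**Step 3. The two missing endpoints**

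| Risk (Table 4, footnote a) | Section 5.4 | Table 3 | Section 5.3 |
|---|---|---|---|
| Acid-base disturbance | absent | absent | absent |
| Acute kidney injury short of dialysis | absent | absent (dialysis only) | absent (dialysis only) |

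**Step 4. Does the 8.5.1 condition explain the missing kidney endpoint?** No. Section 8.4 counts "the development of new or progressive organ dysfunction" as anticipated, so kidney injury falls outside the 8.3 definition and outside a rule about unexpected events. It is missing because no list contains it. Correcting 8.5.1 alone would not capture it.

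**Step 5. Could the outcomes be derived?** Section 5.1.1 abstracts laboratory results with dates and times, and total daily volumes in and out. Both outcomes could be built from the chart where tests were done, but no section defines them or commits to reporting them.

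**The case against.** A limited adverse-event scope is declared openly in sections 1.6 and 8.1, and section 6.3.4 plans no formal safety comparison. That stands, and it limits the consequences. It justifies a short list. It does not justify two incompatible recording rules or the absence of risks that the plan itself names.

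Serious events are reported regardless of relatedness, and the DSMB reviews them. This is a real safeguard. However, the collection sentence in 8.5.1 makes no exception for unlisted serious events, so the text should say which rule prevails. Hypersensitivity is partly covered by rash in Table 3 and by a criterion in 4.6.1 that applies to both arms. The appendices on event timing and the reporting decision tree are not available here and may clarify practice.

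Section 5.1.2 argues for clinically overt outcomes over laboratory findings. That does not explain the omission, since six of the nine 5.4 endpoints are laboratory values. Section 4.6.1 sets creatinine aside partly because testing is intermittent, but that reasoning concerns stopping criteria. It is a fair warning about data quality. Hyperchloremia and hyperlactatemia are also partial proxies for acid-base disturbance.

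A reader might go further and infer that the safety counts will tilt against LR, the less familiar ED fluid. The documents do not support this. Sections 1.2 and 7.1.2 put LR at about half of use in the hospital's PICU, and the background could equally lead staff to suspect NS. A count of the footnoted Table 4 rows alone would seem to show LR risks better covered. Over all rows marked for, or leaning to, one fluid, 3 of 6 NS risks (50%) and 5 of 12 LR risks (42%) have a 5.4 endpoint, counting herniation therapy as cerebral edema. Some LR-only risks, such as bronchospasm, are unlisted too.

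**Conclusion.** Both defects stand in limited form. Sections 8.3 and 8.5.1 contradict each other on recording unlisted unexpected events, and following 8.5.1 makes ascertainment depend on a judgment made with knowledge of the arm. This is a risk of differential ascertainment of unknown size and direction; the counts under working rest on assumed rates. Separately, two comparative risks named in Table 4 are missing from 5.4 and Table 3, so the pilot would neither report them by arm nor test their capture.

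A reader might also use the renal replacement rates of 1.9% and 3.9% in section 1.3.2.2 to argue that almost all lesser kidney injury would go uncounted. Those rates come from a subset described as more severely ill, and the documents give no rate of kidney injury for this population, so that share cannot be estimated.

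The feasibility conclusions are unaffected. The change is worth making because it is cheap and because the 5.4 outcomes are intended for the larger trial.

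**What to change.** 1. In 8.5.1, remove the relatedness condition on collection so that it agrees with 8.3. Record unexpected events in both arms, serious or not, and use relatedness only to decide reporting. Align the appendix diagrams if they say otherwise.
2. Add to 5.4 an acid-base outcome from blood gas or serum bicarbonate, with a stated threshold and the four-day window used for the other laboratory endpoints.
3. Add to 5.4 an acute kidney injury outcome defined identically in both arms. If creatinine is used, state how baseline is set. If urine output is used, note that 5.1.1 abstracts daily total output, so urine may need its own field. Do not rely on the renal criterion in 4.6.1 for ascertainment, because it is written for LR subjects only.
4. Report each outcome by arm with the number of subjects tested, and include both in the 6.3.4 completeness check.

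**Cost.** Wording in 5.4 and 8.5.1, and a few more form lines at the chart reviews already planned. No added tests or visits. Data will be incomplete for subjects not tested, probably most often those admitted to the floor, for whom 4.6.1 says there is no hospital guideline. The number tested would show how incomplete.

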8.5.2 Follow-up report

If an SAE has not resolved at the time of the initial report and new information arises that changes the investigator's assessment of the event, a follow-up report including all relevant new or reassessed information (e.g., concomitant medication, medical history) will be submitted to the IRB. The investigator is responsible for ensuring that all SAE are followed until either resolved or stable.

8.6 Investigator Reporting of a Serious Adverse Event to Sponsor

Reporting will be consistent with all regulatory and sponsor requirements, including the IND submitted to the FDA. [name], a CHOP co-investigator, will be the sponsor for the IND.

8.7 Medical Emergencies

Medical emergencies that might develop during the course of the study will be diagnosed and treated at the discretion of the clinical team.

9 STUDY ADMINISTRATION

9.1 Treatment Assignment Methods

9.1.1 Randomization

Prior to enrollment of any subjects, a complete randomization scheme will be completed using a 1:1 permuted blocks. The randomization sequence will be filed within a series of sequentially numbered, opaque envelopes. A supply cart with both NS and LR will be available where the randomization envelopes are located and will be immediately available for enrollments, so as not to delay treatment of subjects. While not specifically a goal of this study, we do anticipate that the presence of the supply cart may actually enhance the speed of treatment since the fluid will be immediately available at the bedside.

9.1.2 Blinding

Study fluids will not be blinded due to costs and interventions that are not in keeping with a simple, pragmatic trial. Moreover, it may not even be possible to effectively blind clinicians to study fluid assignment due to common electrolyte differences following NS or LR that will suggest a specific fluid selection. This scenario was borne out in the previously published SPLIT fluid trial in which two-thirds of clinicians correctly identified the randomized crystalloid patients received (despite blinding) based on diverging electrolyte profiles.³²

